IRAS code 198005

Figure 2.

Shear and friction relating to DFU is difficult to measure. Custom built tools have had to be used previously to allow appropriate research (Yavuz et al., 2007). There is no common validated reliable device to perform shear or friction evaluations to show effectiveness on healing DFU compared to plantar pressure relief. Therefore it is unrealistic to be able to measure the shear and friction elements associated with DFU within this study and this study will measure downward or a vertical force.

1.2. *Rationale for the proposed study*

Diabetic Foot Ulcer impacts (including cost)

The impacts from diabetes are both patient related and healthcare based. DFU is associated with a high mortality rate at 34% at 1 year. There is an associated higher limb amputation rate from DFU than other causes. The high mortality rate, high amputation rate and increased socio-economic burden means providing high quality evidence based DFU service provision should be a NHS priority. Offloading is recognised as the priority treatment for healing neuropathic and neuro-ischaemic plantar foot ulcers (NICE, 2015). Since the provision of non removable devices or total contact casts (TCC) is poor, options have to be available that are equivalent in effectiveness at off loading and healing DFU. By improving the quality of offloading choices and acceptability for devices this will improve healing rates and reduce the cost burden where currently in the UK diabetic foot care in 2015 accounted for 0.6%/585.5million pounds of the NHS budget (Diabetes UK, 2015, NHS England, 2016). The evidence for effectiveness of non removable devices is poor. Therefore any device that offloads to the equivalent or more than previous devices and current usual standard of care must be evidenced. The new PulseFlow DF boot is such a device which claims to off load but has little or no

Protocol version 1

Evaluating plantar foot pressure in a novel diabetic offloading device

IRAS code 198005

evidence on DFU subjects. Thus the primary aim of this study is to observe forefoot plantar pressures in a cross sectional purposively selected sample compared to usual standard of care.

How pressure relief is studied

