Evaluating plantar foot pressure in a novel diabetic offloading device

IRAS code 198005

pressure time integral could be considered to be of greater significance (Yavuz et al., 2007). Healing requires reducing the pressure over the DFU preventing further tissue damage and promoting healing by redistributing pressure measured by both ppp and pressure time integral. Specialist have debated the issue of both these measurements value and there is no consensus to which one or both to use especially with ppp showing low sensitivity and low specificity to ulcer risk factors (Yavuz et al., 2007, Yavuz et al., 2015, Bus et al., 2016b, Lavery et al., 2003). One of the conclusions was a hypothesis that there must be more complicated diabetic pathology to developing diabetic foot ulceration than just elevated ppp or pressure time integral. The degree of pressure deemed damaging to the DFU is from the length of time in contact (contact time) and the amount of pressure in kPa measured at the interested site(s). It has been highlighted (Ledoux et al., 2013) that there is no consensus on the range of kPa that causes damage (DFU) as studies show numerous variables that affect the measures such as size of pressure cells, static platform or in-shoe measuring devices, site of DFU and sampling techniques within research. Therefore concentrating on the devices used in DFU clinical practice to reduce pressure over DFU sites is more important to heal the skin damage than finding the DFU preventative range of kPa on a patient's foot. The priority is therefore identifying whether this new pressure relieving device changes (redistributes pressure effectively) plantar pressure distribution effectively at the common site (forefoot) of diabetic foot ulcerations.

Sampling Rationale

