2. STUDY AIM AND OBJECTIVES

2.1. Study aim

Protocol version 1

Evaluating plantar foot pressure in a novel diabetic offloading device

IRAS code 198005

The aim of the study is to assess the pressure relief in kPa for pressure time integral (PTI) (Melai et al., 2011) over the forefoot between the boot and usual standard of care.

2.2. *Primary objective*

To identify whether pressure time integral is equivalent or not to usual standard of care.

2.3. *Secondary objective(s)*

To measure the acceptability and effectiveness of the new boot.

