9.2. Hypotheses

Using the novel PulseFlow DF boot is as effective as usual standard care in off loading diabetic plantar forefoot ulcers.

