9.4. Planned analyses

All data will be explored to check for assumptions of normality and homogeneity of variance for each variable, and to assess which statistical tests i.e. parametric or non-parametric test will be more appropriate to explore the data. The assumption of normality will be assessed graphically by histogram, box-plots and confirmed by statistical testing of significance of skewness and kurtosis. The spread, homogeneity and type of data will determine the type of statistical test. The paired t Test is predicted to be the statistical test of choice following statistician advice. This may change due to abnormal distribution of data once collection is complete.

Gait data will be checked for corruption or incomplete results associated with data capture or software error and rectified where possible either at the point of data collection or data analysis.

Exploratory statistical analyses will be performed to identify any potential associations between gait kinematics, clinical data and patient-reported outcomes. We will also explore the data for unexpected findings, including influential outliers, multicollinearity, truncation and missing data.

The primary outcome (section 2.2) will then be compared for systematic differences between the usual standard care and the PulseFlow DF boot using statistical tests based on the assumptions tested previously.

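### The primary objective and hypothesis are framed as equivalence, but section 9.4 plans only a test for a difference, so no planned result can show equivalence and a non-significant result supports neither statement

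*Combined protocol and SAP*

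**What the plan says.** The objective in section 2.2 is "To identify whether pressure time integral is equivalent or not to usual standard of care". The hypothesis in section 9.2, given in the same words in section 1.2, is "Using the novel PulseFlow DF boot is as effective as usual standard care in off loading diabetic plantar forefoot ulcers". The rationale in section 1.2 leans the same way in two places: "options have to be available that are equivalent in effectiveness at off loading and healing DFU" and "any device that offloads to the equivalent or more than previous devices and current usual standard of care must be evidenced".

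Section 9.4 refers to the primary outcome by the number of section 2.2 and says that it "will then be compared for systematic differences between the usual standard care and the PulseFlow DF boot". On the method it says: "The paired t Test is predicted to be the statistical test of choice following statistician advice". The test may change if the data are not normally distributed, but the choice offered is between parametric and non-parametric tests. Section 9.3 lists descriptive summaries (mean, SD, median, range, frequencies) and no confidence interval. No section gives an equivalence or non-inferiority margin, a significance level, or a rule for concluding that the devices are equivalent.

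Other parts of the protocol are framed differently. The full title asks whether the boot reduces plantar pressure, which is a superiority question. The synopsis objective, the outcome statement in 1.2, the aim in 2.1 and the description in 5.1 speak of assessing or comparing pressures.

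**The concern.** A test for a difference takes no difference as its null hypothesis. Rejecting it shows that the devices differ. Failing to reject it shows only that the data did not settle the matter. An equivalence question needs the reverse: a stated margin, and evidence that the true difference lies inside it.

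Here the hypothesis is that the boot matches usual care. If that is true, the expected result of the planned test is non-significance, and the plan does not say what may then be concluded. Whoever writes the report will have an objective that asks about equivalence, a p-value above 0.05, and no planned interval to show how large a difference remains possible.

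This matters even in a proof-of-concept study. Section 5.3 says that the boot should not influence practice or further research until data support it, and section 6.2 says that the study will inform the size of later ones.

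**Working it through.** **Inputs from the documents.** The sample size is 12 in each of three groups (6.2): 12 × 3 = 36, which reproduces the stated total. Each patient is measured in usual care, the boot and the standard shoe (5.1, 6.5.3), so 36 patients give 36 boot-versus-usual-care pairs.

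**Assumptions.** The documents give no significance level, SD or expected difference. I assume a two-sided 5% paired t test on normally distributed differences. I express the true difference d in units of the SD of the paired differences and show a range of values.

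**Step 1: which results could support which statement.**

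| Result of the 9.4 test | Equivalence (2.2) | As effective as (9.2) |
|---|---|---|
| Significant, PTI lower in boot | Answers the negative half: the two are not the same | Supported, if read as at least as effective |
| Significant, PTI higher in boot | Answers the negative half | Contradicted |
| Not significant | Not shown | Not shown |

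No row gives a positive finding of equivalence.

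**Step 2: how often a real difference gives the third row.** With n = 36, the critical value is t(0.975, 35) = 2.030 and the noncentrality is d × √36 = 6d. The chance of a non-significant result is P(−2.030 < T < 2.030), where T is noncentral t with 35 degrees of freedom.

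| True difference d (SD) | Noncentrality 6d | Power | Non-significant |
|---|---|---|---|
| 0 | 0 | 5% (test size) | 95% |
| 0.2 | 1.2 | 21.5% | 78.5% |
| 0.3 | 1.8 | 41.7% | 58.3% |
| 0.4 | 2.4 | 64.6% | 35.4% |
| 0.5 | 3.0 | 83.1% | 16.9% |

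A non-significant result is therefore the usual one when the devices match (95%). It is also more likely than not when they differ by 0.3 SD.

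**Step 3: what a non-significant result leaves open.** The half-width of the 95% confidence interval is t(0.975, 35)/√36 = 2.030/6 = 0.338 SD. A result on the border of significance would have an interval from 0 to 2 × 0.338 = 0.677 SD.

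**Step 4: a smaller sample.** Section 5.2 makes 36 a maximum, with a date cut-off. As an illustration only, with n = 24 the half-width is 2.069/√24 = 0.422 SD, and a true difference of 0.3 SD is missed 71% of the time.

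**The case against.** There are four fair points on the other side.

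- **The difference test is not useless.** Section 2.2 asks whether PTI is equivalent or not, and a significant difference answers the second half. Significantly lower PTI in the boot would support 9.2 read as at least as effective, which fits "any device that offloads to the equivalent or more than previous devices and current usual standard of care must be evidenced" and the superiority question in the title. With a true benefit of 0.5 SD this would happen about 83% of the time at n = 36. This stands, and it rules out saying that the analysis can establish nothing about 2.2 or 9.2.
- **Much of the protocol is not about equivalence.** The title asks about reduction, other sections speak of comparison, and 1.2 also says "The priority is therefore identifying whether this new pressure relieving device changes" pressure distribution. The equivalence sentences in 1.2 are partly background on devices in general. This also stands, but section 9.4 ties its analysis to section 2.2, and 2.2 and 9.2 carry the equivalence wording.
- **This is a single-visit proof-of-concept study.** Its stated primary endpoint is completion of data collection (3.1), and 6.2 calls formal sample-size methods inappropriate. That excuses low power. It does not excuse an objective whose positive answer the analysis cannot give.
- **The data are recoverable.** A confidence interval can be calculated from the same paired data. That is true, and it is why the fix is cheap, but the plan should say so.

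A reader might go further and infer that the investigators intend to read non-significance as equivalence, or that 36 patients is the wrong number. The documents support neither. No section says how a non-significant result will be interpreted, and the sample size is openly a feasibility figure not tied to this test.

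**Conclusion.** The concern holds in a limited form. The analysis in 9.4 can show a difference in either direction, but it cannot give a positive answer to the equivalence question in 2.2. If its result is non-significant, it supports neither 2.2 nor 9.2. No other section supplies the missing margin, interval or decision rule.

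On the assumptions above, true differences of 0.2, 0.3, 0.4 and 0.5 SD would go undetected about 79%, 58%, 35% and 17% of the time with 36 patients, and the 95% interval would reach about 0.34 SD either side of the estimate. These percentages depend on the assumed 5% level and on SD units. The mismatch between objective and analysis does not depend on them. It is a fault of wording and analysis that should be corrected because it affects the only primary objective. It is not a challenge to the design or to the sample size of 36.

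**What to change.** Recast the study as estimation, which suits its purpose of informing later studies.

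1. Restate 2.2 as: To estimate the within-patient difference in forefoot PTI (PulseFlow DF boot minus usual standard care) with a 95% confidence interval.
2. Replace the hypothesis in 9.2, and its copy in 1.2, with that aim.
3. In the last paragraph of 9.4, make the mean paired difference with its 95% confidence interval the primary result. If the non-parametric option is used, report the median paired difference with its 95% confidence interval.
4. Add to 9.4: A non-significant difference will not be interpreted as showing that the boot is equivalent to, or as effective as, usual standard care.

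The patients, measurements and data are unchanged; the cost is rewording and one interval. The downside is that the study could not claim equivalence. If the protocol is already approved, the amendment review in 10.4 and 10.5 applies, including whether the consent document must change and whether patients must be re-consented. The consent pages were not in the text reviewed, so I cannot judge that part.

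The alternative is to keep the equivalence aim, or adopt one-sided non-inferiority, and state the rule in 9.4. That is open only if a PTI margin can be justified before data collection. The documents give no margin and no SD. The nearest statement, "there is no consensus on the range of kPa that causes damage", concerns pressures that damage the foot, not differences between devices.

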9.5. Data Handling

All electronic data will be stored on secure University IT systems with password protected documents backed after each participant entry. All electronic data will be entered in a password protected documented information technology platform internally secured by Leeds Teaching Hospitals and University of Leeds information technology infrastructure. This is on the NHS Leeds Teaching Hospitals F Drive which is a secured server only accessible by named individuals and password protected. In the University of Leeds data will be stored on named individual password protected accounts on the secure server, M Drive. Regular backups of the electronic data will be performed after each entry

Protocol version 1

Evaluating plantar foot pressure in a novel diabetic offloading device

IRAS code 198005

on the secure One Drive at University of Leeds at [name].

All paper copy data will be immediately transferred to electronic format and paper systems shredded as confidential waste.

10. ETHICS AND REGULATORY REQUIREMENTS

10.1. Good Clinical Practice

This study will be conducted in accordance with applicable laws and regulations including, but not limited to, the International Conference on Harmonisation (ICH) Guideline for Good Clinical Practice (GCP) and the recommendations guiding ethical research involving human subjects adopted by the 18th World Medical Assembly, Helsinki, Finland, 1964, amended at the 48th General Assembly, Somerset West Republic of South Africa, October 1996. The Research Ethics Committee (REC) must review and approve the protocol and informed consent form before any subjects are enrolled. Before any protocol-required procedures are performed, the subject must sign and date the REC-approved informed consent form. The right of a patient to refuse participation without giving reasons must be respected. The patient must remain free to withdraw at any time from the study without giving reasons and without prejudicing his/her further treatment. The study will be submitted to and approved by a main Research Ethics Committee (REC) and the appropriate regulatory authorities prior to entering patients into the study.

10.2. Subject information and informed consent

Before being enrolled in the study, subjects must consent to participate after the nature, scope, and possible consequences of the study have been explained in a form understandable to them.

An informed consent document (Patient Information Leaflet) that includes both information about the study and the consent form will be prepared and given to the subject at least 24 hours prior to the screening visit. This document will contain all the elements required by the ICH E6 Guideline for Good Clinical Practice and any additional elements required by local regulations.

At the screening visit, patients will be given the opportunity to ask questions and the nature and objectives of the study will be explained. A podiatry team member caring for the potential participant may help in this process but the principal investigator is responsible for the informed consent discussions.

Protocol version 1**Evaluating plantar foot pressure in a novel diabetic offloading device****IRAS code 198005**

After reading the informed consent document, the subject must give consent in writing. The subject's consent must be confirmed at the time of consent by the personally dated signature of the subject and by the personally dated signature of the person conducting the informed consent discussions.

The original signed consent document will be retained in the study files. Other copies of the consent form are required:

- One copy of the informed consent document will be kept in the patient's clinical notes.
- One copy will be given to the patient.
- One copy will be stored in the master trial file

Consent is an ongoing process and will be reassessed at each study visit.

The Investigator will not undertake any measures specifically required only for the clinical study until valid consent has been obtained.

The Investigator must inform the subject's primary physician about the subject's participation in the trial if the subject has a primary physician and if the subject agrees to the primary physician being informed.

10.3. *Subject confidentiality*

Only the subject number will be recorded in the case report form, and if the subject name appears on any other document (e.g. laboratory report), it must be obliterated on the copy of the document to be supplied to anyone outside the clinical care team. The subjects will be informed that representatives of the Sponsor, Research Ethics Committee (REC) or regulatory authorities may inspect their medical records to verify the information collected, and that all personal information made available for inspection will be handled in strictest confidence.

All information collected during the course of the trial will be kept strictly confidential.

Information will be held securely on paper and electronically. All paper hard copies with patient identifiable data will be kept in the trial master file locked in a filing cabinet within a locked staff only access room on the NHS clinical site where consent is being taken (Chapel Allerton Hospital). All data transferable to electronic format will be performed directly after any paper data collection and the paper data destroyed as confidential waste. A site file at the recruiting centre (Leeds Teaching Hospitals NHS Trust) will store only copies of information for the participants and research protocol information accessible to staff within the team treating potential participants.

The University of Leeds via the Chief Investigator will comply with all aspects of the Data Protection Act 1998.

Protocol version 1

Evaluating plantar foot pressure in a novel diabetic offloading device

IRAS code 198005

The Principle Investigator at each site will maintain a personal subject identification list (subject numbers with the corresponding subject names) to enable records to be identified.

10.4. Approval of clinical study protocol and amendments

Before the start of the study, the clinical study protocol, informed consent document, and any other appropriate documents will be submitted to the REC and the Sponsor with a cover letter or a form listing the documents submitted, their dates of issue, and the site (or region or area of jurisdiction, as applicable) for which approval is sought.

Before the first subject is enrolled in the study, all ethical and legal requirements must be met, including approval of the study by the NHS, the Sponsor Research and Development department and the REC.

Amendments must be evaluated to determine whether formal approval must be sought and whether the informed consent document should be revised, thus all protocol amendments and administrative changes must first be discussed with and approved by the Sponsor before being submitted to the REC, in accordance with legal requirements. Amendments must be evaluated to determine whether formal approval must be sought and whether the informed consent document should be revised.

The Investigator must keep a record of all communication with the REC and the Sponsor.

10.5. Protocol amendments

Requests for any amendments to the study must be sent to the Sponsor by the Principal and Chief Investigator. The Sponsor will determine whether said amendments are substantial or non-substantial prior to their submission to the appropriate bodies for approval. Patients should be re-consented to the study if the amendments affect the information they have received, patient safety, or if the change alters the type or quality of the data collected for the study. Patients should only be re-consented AFTER an amendment has been fully approved.

10.6. Ongoing information for Research Ethics Committee

Unless otherwise instructed by the REC and the Sponsor, the Investigator must submit to the REC and the Sponsor:

- Information on serious adverse events that are unexpected and related to study procedures (RUSAEs) from the Investigator's site, within 15 calendar days of the research team becoming aware of them.

Protocol version 1**Evaluating plantar foot pressure in a novel diabetic offloading device****IRAS code 198005**

- Expedited safety reports, as soon as possible.
- Annual reports on the progress of the study.
- The NRES Declaration of End of Study form.

11. FINANCE AND INSURANCE

11.1. Indemnity and insurance

UoL sponsored study: The University of Leeds is able to provide insurance to cover for liabilities and prospective liabilities arising from negligent harm. Clinical negligence indemnification will rest with the participating NHS Trust or Trusts under standard NHS arrangements.

